7.9.2 Pharmacodynamics

At select sites, blood samples from each consenting participant will be analyzed onsite using Light Transmission Aggregometry (LTA) under non-GLP conditions at baseline and select time points following the start of the study drug administration as specified in **Section 6.6.3**.

The following will be measured:

- Inhibition of platelet aggregation (maximum and final) induced by SFLLRN 5-20 μM (or SFLLRN of equivalent potency) using blood collected in 0.4% sodium citrate.
- Inhibition of platelet aggregation (maximum and final) induced by AYPGKF 160 μM using blood collected in 0.4% sodium citrate.
- Inhibition of platelet aggregation (maximum and final) induced by collagen 4-20 $\mu\text{g/mL}$ using blood collected in 0.4% sodium citrate.
- Inhibition of platelet aggregation (maximum and final) induced by 5-20 μM ADP using blood collected in 0.4% sodium citrate.
- Inhibition of platelet aggregation (maximum and final) induced by thrombin 1 nM-1 μM using blood collected in 0.4% sodium citrate (with GPRP added for 1mM final concentration).

Maximal and final extent inhibition of platelet aggregation (IPA) from pre-dose baseline at Screening will be calculated at all subsequent time points using

$$\text{Percentage of Inhibition} = 100\% \times \frac{(\text{PAs} - \text{PA})}{(\text{PAs})}$$

Where PA is the mean response at the given time point, and PAs is the mean response at pre-dose baseline (Screening). Percentage inhibition will be restricted to the closed interval [0,100]; any data falling outside this range will be truncated to the appropriate limit. Individual peak inhibition of platelet aggregation (IPA_{max}) will be estimated as the highest IPA within the collection time period and TIPA_{max} will be the time to IPA_{max} for final extent and maximum extent of IPA.

The percentage inhibition of the specific agonist-induced platelet aggregation (final and maximum extent) will be summarized at the scheduled protocol time points using standard summary statistics for each treatment group. Mean plots showing changes within treatment groups across time will be presented. The derived PK and PD parameters will be summarized using standard summary statistics and graphical presentations.

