Currently, the only effective agent preventing thromboxane A₂ generation is aspirin (ASA). Although ASA does not impact strong agonists like thrombin or collagen-dependent platelet activation under high arterial shear stress, it lowers the risk of cardiovascular events in subjects with established cardiovascular disease by approximately 25%. ASA is first-line antiplatelet therapy [6]. ADP is an agonist for the platelet P₂Y₁ and P₂Y₁₂ receptors and is a key cofactor in platelet activation induced by thrombin and collagen, which results in release of more ADP. Clopidogrel is a pro-drug yielding an active metabolite that binds irreversibly to the P₂Y₁₂ receptor. In the Clopidogrel in Unstable angina to prevent Recurrent Events (CURE) study, the addition of clopidogrel to ASA reduced the incidence of the composite of cardiovascular death, non-fatal MI, or stroke by 20% relative to ASA alone (9.3% vs 11.4%) in subjects mainly receiving medical treatment for non-ST-segment-elevation acute coronary syndrome (NSTEMI-ACS); however, the combination also resulted in a modest increased risk of major bleeding (3.7% vs 2.7%) [7]. Among the subset of subjects who received PCI, the incidence of minor bleeding was greater among those who received clopidogrel (3.5%) rather than placebo (2.1%) [8]. Pharmacodynamic studies evaluating antiplatelet responses in subjects undergoing stenting have revealed various limitations of P₂Y₁₂ inhibition such as a delayed or irreversible pharmacodynamic response; distinct subject-to-subject response variability with a substantial percentage of subjects exhibiting non-responsiveness; and a potential influence of drug-drug interactions [9]. Compared with clopidogrel, new and more potent oral P₂Y₁₂ inhibitors such as prasugrel and ticagrelor reduce the risk of ischemic events by ~20% in subjects with acute coronary syndrome (ACS) [10, 11]. However, intensified blockade of P₂Y₁₂ with new P₂Y₁₂ agents may be associated with elevated bleeding and potentially other side effects such as dyspnea [12]. In this regard, ASA and P₂Y₁₂ receptor antagonists inhibit platelet aggregation induced by collagen, TXA₂ and ADP, properties that may interfere with normal hemostasis. The slow offset of P₂Y₁₂ inhibition by all currently

approved oral agents may be problematic in subjects requiring coronary artery bypass graft surgery [13].

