5.4 Other Secondary Objectives Related to Efficacy

Other secondary efficacy objectives will include evaluation of PZ-128 in terms of the following:

1. incidence of the individual components of the MACE composite as measures of potential clinical benefit;
2. incidence of definite or probable stent thrombosis as a measure of potential clinical benefit;
3. inhibition of platelet aggregation induced by SFLLRN (PAR1 agonist) and thrombin as an indicator of the desired pharmacodynamic effect, and ADP (adenosine diphosphate), collagen and AYPGKF (PAR4 agonist) to evaluate the specificity of PZ-128;
4. effect of the investigator choice of P2Y₁₂ inhibitor on the individual components of the MACE composite; and

5. population pharmacokinetics.

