6.4.3 Other Required and Potential Rescue Treatment(s) (Standard of Care)

Investigators will use current applicable standard of care guidelines, the individual's clinical circumstances, and the local practices for the procedures surrounding the cardiac catheterization ± PCI and follow-up care post cardiac catheterization ± PCI [47].

Standard of care treatments/parameters in the context of this study will include oral anti-platelet therapy- aspirin and P2Y₁₂ inhibitor (i.e., clopidogrel, prasugrel, or ticagrelor), an anti-coagulant (i.e., unfractionated heparin or low-molecular-weight heparin) and potential rescue therapy (thrombotic bailout) with a GP IIb/IIIa inhibitor (e.g., eptifibatide). These treatments administered/taken within 30 days prior to randomization and at any time during the study must be documented in the subject's source documents/medical records and recorded in the "Previous and Concomitant Medication" module of the eCRF.

- **Aspirin:** Subjects not on aspirin therapy should be given nonenteric aspirin 325 mg before the study drug administration (subjects already taking daily aspirin therapy should take 81-325 mg before the study drug administration). After the cardiac

catheterization/PCI aspirin 81-325 mg daily may be continued indefinitely. ASA for pain relief should where possible be discouraged and acetaminophen given.

- **P2Y₁₂ Inhibitor(s):** A loading dose of an FDA-approved oral P2Y₁₂ inhibitor should be given to subjects before PCI with stenting (dosing may be adjusted depending upon prior chronic use of oral P2Y₁₂). Investigator discretion will be used and options include the following:
 - Clopidogrel (Plavix[®]) 600 mg
 - Prasugrel (Effient[®]) 60 mg
 - Ticagrelor (Brilinta[®]) 180 mg

The choice and duration of oral P2Y₁₂ inhibitor therapy after stent implantation will be as per investigator discretion. Options include the following FDA-approved drugs:

- Clopidogrel (Plavix[®]) 75 mg daily
 - Prasugrel (Effient[®]) 5-10 mg daily
 - Ticagrelor (Brilinta[®]) 90 mg twice daily
- **Anticoagulant:** An anticoagulant should be administered to subjects undergoing PCI. Following administration of the initial bolus of anticoagulant, activated clotting time (ACT) will be measured locally at “peak dose” and just prior to sheath removal, as well as according to the standard of care.

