One blood sample for DNA, RNA and microRNA analysis will be collected just before the administration of the study drug. Pharmacogenomics analysis will be undertaken to investigate whether DNA polymorphisms, RNA levels and microRNAs correlate with the expression of genes involved in thrombosis, inflammation, and cardiometabolic diseases and whether these genetic components correlate with PZ-128 outcomes. The samples will be analyzed by the sponsor and/or at one of the participating clinical sites under non-GLP conditions.

Subjects at Select Clinical Site(s) Participating in the PK/PD Sub-study

- **Pharmacodynamics- Platelet Aggregation (Whole Blood): Just Prior to Study Drug Infusion, Select Times During Hospitalization, 24-hour/Discharge, 14-day Visit**

Blood samples will be collected just before the administration of the study drug, then 30 minutes \pm 5 min, 1 hour \pm 5 min, 2 hours + 15 min (immediately after completion of infusion), 6 hours – 2 h (4 to 6 h) and 24 hours \pm 2 h or discharge (whichever occurs sooner) after the start of the study drug infusion and at the 14-day visit. After the 24-hour collection, if a subject remains in the hospital for \geq 48 hours, a blood sample will be collected just prior to discharge. The samples will be analyzed using light transmission aggregometry (LTA) on-site under non-GLP conditions.

- **Pharmacokinetics (Plasma): Just Prior to Study Drug Infusion, Select Times During Hospitalization, 24-hour/Discharge, 14-day Visit**

Blood samples will be collected just before the administration of the study drug, then 30 minutes \pm 5 min, 1 hour \pm 5 min, 2 hours + 15 min (immediately after completion of infusion), 6 hours – 2 h (4 to 6 h) and 24 hours \pm 2 h or discharge (whichever occurs sooner) after the start of the study drug infusion and at the 14-day visit. After the 24-hour collection, if a subject remains in the hospital for \geq 48 hours, a blood sample will be collected just prior to discharge. The samples will be analyzed by the sponsor/sponsor's designee under non-GLP conditions.

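### Percent platelet inhibition is divided by pre-dose aggregation with no provision for low or zero baselines, which weakens the ADP and collagen specificity readout when some subjects are already suppressed.

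*Combined protocol and SAP*

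**What the plan says.** Section 7.9.2 (Pharmacodynamics) gives one formula, IPA = 100 × (PAs − PA)/PAs, for all five agonists and for both maximal and final aggregation. The terms are defined thus: "Where PA is the mean response at the given time point, and PAs is the mean response at pre-dose baseline (Screening". Out-of-range values are handled by this rule: "Percentage inhibition will be restricted to the closed interval [0,100]; any data falling outside this range will be truncated to the appropriate limit". A per-subject peak follows: "Individual peak inhibition of platelet aggregation (IPA_{max}) will be estimated as the highest IPA within the collection time period". Results are summarised descriptively by treatment group. The section has no rule for a zero or low PAs and no analysis of absolute aggregation.

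Section 5.4 uses ADP, "collagen and AYPGKF (PAR4 agonist) to evaluate the specificity of PZ-128".

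On timing, Section 6.6.3.2 states for the aggregation samples: "Blood samples will be collected just before the administration of the study drug, then 30 minutes". The flow chart in Section 1.2 shows no pharmacodynamic sample at Screening. Section 6.5.3 lists aspirin ahead of that pre-infusion sample.

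On background treatment, Section 6.4.3 says of the P2Y12 loading dose that "dosing may be adjusted depending upon prior chronic use of oral P2Y₁₂", and Section 6.3.2 does not exclude prior users. Section 4.1.1 says that aspirin and P2Y12 "receptor antagonists inhibit platelet aggregation induced by collagen", thromboxane A2 and ADP.

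**The concern.** A ratio to baseline behaves well only while the baseline is large relative to assay error. By the protocol's own account, the background drugs lower the response to two of the three specificity agonists, and some of that lowering can precede the baseline sample. Final aggregation at the lowest concentrations listed (5 µM ADP, 4 µg/mL collagen) is the likeliest place for small denominators.

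Three things follow for such subjects. A change of a few aggregation points becomes a large percentage. One-sided truncation turns symmetric noise into apparent inhibition, and IPAmax, as a maximum over several samples, amplifies it. A subject with PAs = 0 has no value at all.

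For ADP and collagen the expected answer is no effect. A metric that drifts above zero without a drug effect, and carries extra noise, is poorly suited to showing that.

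**Working it through.** The plan states no power, baseline level or assay SD for this endpoint, so there is no figure to reproduce. Every level and SD below is an assumption.

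**1. By hand, using the Section 7.9.2 formula.**
- PAs = 50, PA = 48: 100 × 2/50 = 4%.
- PAs = 4, PA = 2: 100 × 2/4 = 50%. The change is the same two points.
- PAs = 4, PA = 6: 100 × (−2)/4 = −50%, recorded as 0.
- Symmetric noise of ±2 points therefore averages (50 + 0)/2 = 25% at PAs = 4, and (4 + 0)/2 = 2% at PAs = 50.
- PAs = 0: division by zero, which truncation does not resolve.

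**2. Fixed true baseline, no drug effect.** 200,000 simulated subjects, one baseline and six later readings, aggregation limited to 0–100, IPA truncated. Main figures use assay SD 5; brackets show assay SD 3 to 8.

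| True baseline (%) | Undefined (%) | Mean IPA (%) | SD of IPA | Mean IPAmax (%) |
|---|---|---|---|---|
| 70 | 0 | 3.8 (2.3–5.9) | 5.4 (3.4–8.4) | 9.3 (5.6–14.5) |
| 30 | 0 | 8.3 (5.2–12.6) | 11.7 (7.4–17.5) | 20.7 (12.8–32.2) |
| 20 | 0 (0–0.7) | 11.9 (7.6–18.0) | 16.6 (10.7–24.5) | 30.2 (18.8–47.1) |
| 10 | 2.3 (0–10.5) | 22.0 (13.9–31.7) | 29.0 (19.3–37.1) | 57.5 (35.9–78.8) |
| 5 | 15.8 (4.9–26.6) | 36.8 (25.5–45.9) | 39.9 (32.4–43.0) | 86.1 (66.3–94.3) |

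The instability is serious at about 10% or below and modest at 30% or above. The upward bias from truncation is present throughout.

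**3. Mixed population.** Suppressed subjects have baseline mean 8 (SD 6), the others mean 50 (SD 12), assay SD 4. The treated arm's true post-dose level is 0.8 × baseline, a 20% off-target effect. Separation for IPA is the difference in means divided by the pooled SD. For adjusted absolute aggregation it is the treatment coefficient divided by the residual SD, from a regression of post-dose aggregation on arm and pre-dose aggregation.

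| Share suppressed | Undefined (%) | Mean IPA, no effect (%) | SD of IPA, no effect | Separation, IPA | Separation, adjusted absolute |
|---|---|---|---|---|---|
| 0% | 0 | 4.5 | 6.8 | 1.73 | 1.86 |
| 10% | 1.1 | 6.4 | 13.3 | 1.03 | 1.65 |
| 20% | 2.3 | 8.2 | 17.4 | 0.79 | 1.48 |
| 30% | 3.4 | 10.1 | 20.5 | 0.65 | 1.33 |

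At 20% suppressed, IPA moves from 8.2 to 22.3 with a pooled SD of about 18: 14.1/18 ≈ 0.79. The adjusted difference is 8.31 points with residual SD 5.61: 8.31/5.61 = 1.48. For equal precision IPA would need about (1.48/0.79)² ≈ 3.5 times as many subjects.

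**4. Sensitivity at 20% suppressed.** With assay SD 3 the separations are 0.94 and 1.87; with assay SD 8 they are 0.50 and 0.80. With a 50% off-target effect and assay SD 4 they are 2.34 and 2.96, so the advantage shrinks when the effect is large.

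**The case against.** A reader might infer that pre-dose ADP and collagen aggregation is zero or near zero in everyone on aspirin and a P2Y12 inhibitor, so that the specificity readout is undefined or mostly noise in them. The documents do not support that. They give no baseline value. Section 4.1.1 gives a direction without a size, and it describes variable P2Y12 response with a substantial share of non-responders. In phase 1 (Section 4.1.2.2), ADP and collagen were read out with 20 of 31 treated subjects (65%) on aspirin. The loading dose before PCI comes after the baseline sample, so a P2Y12 effect at baseline needs prior use, whose frequency is not stated. The panel also includes maximal aggregation, higher concentrations and AYPGKF, and nothing says the background drugs suppress AYPGKF responses. Large negative percentages would never be reported, since the plan records them as 0.

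It is also fair to say that changing the metric does not restore signal where little aggregation is left. If every subject were suppressed, a 50% effect would separate the arms by 0.74 SD on IPA, 0.72 on unadjusted absolute change and 0.90 with baseline adjustment. That stands: the clear gain appears when suppressed and unsuppressed subjects are pooled.

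Placebo should share the bias. This protects the between-arm difference but not its precision, and the planned plots of change within groups have no such protection. Section 7.2 defers data-handling conventions to a later SAP, which is the right place for a rule. Finally, the formula's reference to mean responses might suggest a ratio of group means, but the individual IPAmax implies a per-subject calculation.

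**Conclusion.** The point holds in a limited form. The formula lacks a low-baseline rule, the design allows low ADP and collagen baselines in some subjects, and truncation biases mean IPA and IPAmax upward without any drug effect. IPA is undefined only when PAs is exactly 0.

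With 20% of subjects suppressed and assay SD 4, separation for a 20% off-target effect is roughly halved (about 0.8 against 1.5 SD), and mean IPA is about 8% with no effect. These sizes rest on assumed baselines, assay SD and share suppressed; with nobody suppressed the two methods are close (1.73 against 1.86 SD).

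The endpoint is secondary, descriptive and confined to an optional sub-study at select sites. The primary bleeding analysis and the sample size are unaffected. The change is worth making because it is a better analysis of data already being collected.

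**What to change.** In Section 7.9.2 or the SAP:

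- For each agonist, compare absolute aggregation (maximal and final) at each time point between PZ-128 and placebo, with the pre-infusion value as covariate.
- Keep percent IPA and IPAmax as descriptive companions, reported only for subjects whose pre-dose aggregation to that agonist reaches a prespecified minimum. Set that minimum from assay precision; 20% is only an example, with no basis in the documents. Report the number excluded by arm.
- State that baseline is the pre-infusion sample and remove the Screening label, because no pharmacodynamic sample is drawn at Screening.

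The cost is a change of wording before unmasking, with no new data. The downside is that percent IPA will be reported on fewer subjects for ADP and collagen.

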After written informed consent is obtained, eligibility tests/evaluations will be performed. All screening assessments must be completed prior to randomization and be within 14 days of the study drug treatment (this may include standard of care preadmission testing for the planned procedure). For the purposes of this study, a subject is considered enrolled into the trial upon successful randomization and an assignment of study drug and a unique subject randomization number. On the day of the procedure, subjects will receive a dose of aspirin (81-325 mg) orally. Subjects will receive the randomized assignment of PZ-128 or matching placebo as a single, 2-hour continuous IV infusion, to be initiated within 1 hour prior to the start of the cardiac catheterization procedure (defined as the time of the arterial sheath placement prior to the diagnostic angiography) in a 2:2:1:1 parallel, double-blind fashion of either: **1) PZ-128 0.3 mg/kg, 2) PZ-128 0.5 mg/kg, or 3) Placebo 0.3 mg/kg, or 4) Placebo 0.5 mg/kg.**

If PCI is deemed necessary and appropriate during catheterization, an anticoagulant (unfractionated heparin or low-molecular-weight heparin) will be added and a loading dose of an oral P2Y₁₂ inhibitor (clopidogrel, prasugrel or ticagrelor) will be administered per investigator choice and standard of care guidelines before PCI. All other subsequent therapy or care provided and not specified by the protocol will be in accordance with the local standard.

PCI successfully begins when the guide wire crosses the lesion, regardless of any subsequent event or process, including completion of the intended procedure. The planned treatment with any GP IIb/IIIa Inhibitor (GPI) during the PCI will not be allowed, but investigators may use these agents as a thrombotic bailout if indicated. Following the procedure, subjects will be advised regarding continuing/maintenance treatment with aspirin and a P2Y₁₂ inhibitor according to local standard of care.

If a PCI is not indicated during catheterization, or is indicated but does not commence (guide wire does not cross the lesion) for any reason, the subject will undergo medical management or surgical revascularization (i.e., CABG) according to the local standard of care.

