6.5.3 Pre-Cardiac Catheterization Procedure

1. Prepare study drug for administration in investigational/research pharmacy (see *Investigational Product Instruction Manual-IPIM*).
2. Record any changes to concomitant medication(s).
3. Confirm subject still meets eligibility criteria to receive study drug.
4. Perform and document urine pregnancy test (urine beta-HCG point-of-care test) for women of child-bearing potential if screening assessment was not within the 24 hours prior to study drug administration. The result must be known and negative prior to administration of the study drug.
5. Administer aspirin.
6. 
7. Obtain vital signs, including heart rate and blood pressure just prior to study drug administration (i.e., Time=0).
8. Collect blood sample (serum) for centralized research analysis of Cardiac Troponin I (cTnI) just prior to study drug administration (i.e., Time=0).
9. Collect blood samples for optional research according to site participation and subject's individual consent (see **Section 6.6.3.2**) just prior to study drug administration (i.e., Time=0):
 - a. Samples for pharmacokinetics (plasma) and pharmacodynamics-platelet aggregation (whole blood) (PK/PD sub-study; participating sites only);
 - b. Plasma sample for exploratory biochemical, inflammatory and metabolic markers; and
 - c. Whole blood sample for pharmacogenomics.
10. **Start blinded PZ-128/placebo** IV administration 0-60 min prior to start of coronary angiography and infuse continuously over 2 hours (infuse entire contents for complete dosing). Observe anaphylaxis precautions during the infusion and for at least 1 hour following cessation of study drug.
11. Perform any additional standard of care assessments in the pre-cardiac catheterization/PCI setting.
12. Assess and record adverse events, including bleeding and clinical efficacy endpoint events (MACE, stent thrombosis).

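### Section 7.9.2 specifies no PZ-128-minus-placebo contrast for platelet inhibition although P2Y12 loading starts after baseline, so per-arm values alone cannot answer the specificity objective

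*Combined protocol and SAP*

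**What the plan says.** Section 5.4 uses SFLLRN and thrombin to measure the wanted effect, and ADP, "collagen and AYPGKF (PAR4 agonist) to evaluate the specificity of PZ-128". IPA is the third of the other secondary efficacy endpoints in section 6.7.1.4.

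Section 7.9.2 defines percent inhibition as 100% × (PAs − PA)/PAs, forced into the range 0 to 100. The results "will be summarized at the scheduled protocol time points using standard summary statistics for each treatment group", and "Mean plots showing changes within treatment groups across time will be presented". Individual peak inhibition (IPAmax) "will be estimated as the highest IPA within the collection time period", with the time of that peak (TIPAmax) alongside. The section gives no between-group estimate, no confidence interval and no basis for judging specificity.

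Two other places go further. Section 7.9.3 says biomarker changes are to be compared between treatment groups. The Statistical Methods part of the synopsis says comparisons for secondary endpoints will be made for PZ-128 pooled and by dose.

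On background therapy, section 6.1 says that if PCI is chosen during catheterization, a loading dose of an oral P2Y12 inhibitor "will be administered per investigator choice and standard of care guidelines before PCI". Section 6.4.3 notes that "dosing may be adjusted depending upon prior chronic use of oral" P2Y12 treatment. A GP IIb/IIIa inhibitor (GPI) may be used as thrombotic bail-out.

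On baseline, section 7.9.2 states "PAs is the mean response at pre-dose baseline (Screening", while section 6.5.3 has the sample drawn "just prior to study drug administration (i.e., Time=0". The flow chart in section 1.2 schedules no pharmacodynamic sample at Screening.

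**The concern.** A change from the subject's own baseline isolates the study drug only if nothing else that affects aggregation starts after baseline. Here something does, in the subjects who go on to PCI. Section 4.1.1 states that P2Y12 antagonists inhibit aggregation induced by ADP and collagen, which are two of the three agonists used to judge specificity. The per-arm summaries that section 7.9.2 asks for will therefore contain background inhibition. The same applies to the within-group plots.

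At stake is how the specificity objective is read. The randomised placebo group carries the same background therapy, so the difference from placebo answers the question. The operative section does not name that difference or attach any uncertainty to it. The peak summary has a related weakness, since its search window takes in samples where background therapy may dominate.

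**Working it through.** The plan gives no figure to reproduce: it states no pharmacodynamic sample size, standard deviation or expected IPA. The check has two parts: the timing, which rests on the documents, and an illustration of size, which rests partly on assumptions.

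**Timing.** Infusion starts 0 to 60 min before catheterization (section 6.1). Time since the start of catheterization at a sample is therefore the sample time minus 0 to 60 min. Sample times are in the notes to section 1.2; collection windows are ignored here.

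| Sample after start of infusion | Time since start of catheterization |
|---|---|
| Time 0 | not started, or just starting |
| 30 min | −30 to +30 min |
| 1 h | 0 to 60 min |
| 2 h | 60 to 120 min |
| 4-6 h | 180 to 360 min |
| 24 h or discharge; day 14 | after the procedure; stented subjects may be on maintenance P2Y12 therapy |

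The 30 min and 1 h samples may precede the load. From about 2 h the load can be expected to be on board in PCI subjects. Aspirin is step 5 of section 6.5.3 and the baseline draw is step 9, so aspirin is listed before baseline.

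**Size of the background component (illustration).** Let s be the share of subjects newly loaded after baseline and d the inhibition that loading produces. With no PZ-128 effect on the agonist, the arm mean is s × d.

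- The only figure in the documents for s is 56% (573/1030 = 0.556), the share proceeding to PCI in the earlier phase 2 PAR1-antagonist trial in section 4.1.1. It is borrowed, and it overstates s where subjects already take a P2Y12 inhibitor.
- The documents give no value for d. Assumed range: 20 to 60 points.
- At s = 0.56: 0.56 × 20 = 11.2; 0.56 × 40 = 22.4; 0.56 × 60 = 33.6 points.
- Wider range: 0.3 × 20 = 6.0 up to 0.8 × 60 = 48.0 points.
- Simulated with noise SD 10 or 20 and the plan's clipping, the arm mean is 13 to 37 at s = 0.56, and about 9 to 50 over the wider range. Placebo shows the same values, and the difference is 0 to within 0.1 point.

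For scale, section 4.1.2.2 gives 20-40% inhibition of PAR1 aggregation at 0.3 mg/kg in phase 1.

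**Clipping.** If true inhibition is zero and noise is normal with SD σ, the mean after clipping at zero is σ/√(2π) = 0.399σ: 4.0 points at σ = 10 and 8.0 at σ = 20. Around zero, where specificity is judged, the clipped mean moves by only about half of a small true change, because half the values sit at the limit. Clipping therefore also shrinks a small real off-target difference between arms.

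**Peak.** In phase 1 the drug was undetectable in plasma at 24-192 h (section 4.1.2.2), yet the collection period runs to day 14 (section 6.6.3.2). As a noise-only illustration, assume baseline and six post-dose values around 70 with SD 5 or 10. The mean clipped peak is then 9.3 or 18.0 points with no effect of any drug. It falls on one of the last two samples in 2/7 = 28.6% of subjects. That fraction is just the chance that one of two named values is the lowest of seven exchangeable ones. It applies equally to placebo and does not measure the influence of background therapy.

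**The case against.** The strongest reply is that the information is already there. Placebo is one of the treatment groups summarised, its two arms are merged for analysis (section 7.1), and it is randomised and concurrent. The synopsis promises comparisons for secondary endpoints, and section 7.2 leaves detail to a SAP written before unmasking. All of this stands. A reader might infer that the plan will wrongly declare PZ-128 non-selective. The documents do not support that: the same background inhibition would appear in the placebo row of the same table. What remains is that neither the synopsis nor section 7.9.2 defines the contrast or its interval.

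A reader might also infer that aspirin starts between baseline and the later samples. The visit sequence puts it before the baseline draw. It could contribute only if its effect were still developing at Time 0, or if the Screening label were taken literally.

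Other limits also stand. Section 4.1.1 lists a delayed response among the limitations of P2Y12 inhibition, so one value of d for all times is a simplification. The documents give no P2Y12 effect on the PAR4 agonist AYPGKF, and do not say how a GPI alters each readout. Undetectable plasma drug does not mean no effect: section 4.1.2.2 reports only 40% recovery of aggregation to 8 μM PAR1 agonist at 24 h in aspirin-treated subjects at 0.5 mg/kg. The 24 h sample therefore should not simply be discarded. Finally, this is an optional sub-study at selected sites, presented descriptively.

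**Conclusion.** The concern holds as a gap in specification. Per-arm ADP and collagen inhibition from about 2 h onward mixes background therapy with any PZ-128 effect, and cannot by itself answer the specificity objective. This follows from the stated timing and from section 4.1.1, without assumed figures. The size is only illustrative: 11 to 34 points at 56% loaded and an assumed 20 to 60 points from loading, similar in scale to the phase 1 PAR1 effect at 0.3 mg/kg. The drug-minus-placebo difference removes it.

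Two details of section 7.9.2 add to the problem. Clipping biases values near zero upward and compresses small differences. The peak search can select the 24 h or day-14 sample. The baseline label also conflicts with the sampling schedule and must be reconciled. The change should be made, but nothing here touches the primary bleeding analysis.

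**What to change.** In section 7.9.2 and the SAP:

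- For each agonist and time point, report the PZ-128 (pooled and per dose) minus pooled-placebo difference with a 95% confidence interval, from unclipped aggregation adjusted for the Time 0 value. Judge specificity on the ADP, collagen and AYPGKF differences. Keep percent IPA, the endpoint as defined in section 6.7.1.4, as a descriptive summary.
- Define baseline as the Time 0 sample and reconcile the Screening label with sections 1.2 and 6.5.3.
- Limit IPAmax and TIPAmax to samples through 4-6 h, with the 24 h sample added in a sensitivity analysis.
- Show results descriptively by timing of P2Y12 treatment relative to each sample (chronic at baseline, loaded before the sample, none).
- Exclude samples drawn after a GPI only in a sensitivity analysis. Bail-out follows randomisation and is given for ischemic or thrombotic complications that PZ-128 might affect, so excluding those samples from the main analysis could introduce selection.

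The cost is SAP wording and a few more tables. Placebo samples and concomitant drug records are already collected. Section 6.4.8.1 asks for start and stop dates, so clock times for the P2Y12 load and any GPI would need to be captured for sub-study subjects.

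Intervals will be wider than for within-arm means. With equal SDs and the 2:2:1:1 allocation kept in the sub-study, write m for the pooled placebo number; pooled PZ-128 then has 2m subjects and each dose m. Before covariate adjustment, the standard error grows by √[(1/2m + 1/m)/(1/2m)] = √3 = 1.73 for pooled PZ-128 and by √2 = 1.41 for each dose.
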